1.4 Trial Intervention

Patient screened for eligibility (during kidney transplant workup / whilst on transplant waiting list)

Discuss study with patient and or parent/guardian

Obtain informed consent from patient (if ≥16 years old) or from parent/guardian (if <16 years old) and patient assent where appropriate

Randomisation (just prior to the kidney transplant)

CONTROL GROUP

(72 patients)

Standard intravenous fluid therapy intra- and post-operatively, as required

STUDY GROUP

(72 patients)

Plasma-Lyte-148 / Plasma-Lyte-148 5% glucose intra- and post-operatively, as required

Kidney transplant operation performed as per standard practice, with fluid therapy according to the randomisation

Follow-Up Data Collection

Day 1, Day 3 and Day 7 post-transplant

Blood results*, fluid requirements, post-operative symptoms.

*Post-operative blood sampling as per standard practice (all results, up to Day 3, for the following tests will be collected: sodium, potassium, urea, creatinine, chloride, bicarbonate, magnesium, glucose, haemoglobin. The GOSH Digital Research Environment Team will assist with the collation of this data).

Up to Day 90

Date of discharge

Transplant kidney function will be obtained directly from the UK Transplant Registry, held by NHS Blood and Transplant at Day 90

Statistical Analysis Plan

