All tests will be two-sided, p-values of less than 0.05 will be considered as evidence of a difference between treatment arms, and conditional effects will be reported. P-values will be reported to four decimal places with p-values less than 0.0001 as <0.0001. All confidence intervals presented will be 95% and two-sided. Exact confidence intervals will be used for binary data, where exact models have been used. Multiple comparisons will be performed and this may increase the probability of observing a statistically significant result by chance. No adjustments will be made to account for multiple testing. The statistical package SAS will be used to conduct analyses.

The key demographics and clinical condition of the participants will be presented for each arm of the trial to describe the cohort. In addition, a summary of transplant characteristics will be presented for each arm of the trial. A CONSORT diagram will be presented to show how participants progressed through the trial.

All analyses and accompanying tables will be presented by the treatment to which the participant was randomised. All odds, hazard and rate ratios will be presented as Plasmalyte arm versus Standard arm. A ratio which is greater than 1 indicates that the odds, hazard or rate of the event is greater in the Plasmalyte arm. 95% confidence intervals will be presented with all ratios.

P-values for regression models will be obtained by comparing models with and without the treatment term using the likelihood ratio test. In analyses where mixed models are performed, the log-likelihood will be estimated using pseudo-likelihood methods.

All analyses will be adjusted for the stratification variables (site and participant weight pre transplant: <20kg and ≥20kg) and donor type: deceased and living, as this was also felt to be an important factor which could affect the outcomes of interest. Site will be

Statistical Analysis Plan

accounted for by including a random effect and participant weight and donor type by a fixed effect in each model.

Although PLUTO is a definitive trial, the total sample size is relatively small, hence:

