A repeated measures mixed Normal linear regression will be used to assess whether kidney function over days 1,3 and 7 are different between the two treatment arms, adjusting for donor type (living vs deceased donor), participant weight pre transplant (<20kg vs ≥20kg pre-transplant) and day of measurement. In addition, two random

Statistical Analysis Plan

effects will be included in the model to account for individual participant effects and transplant centre. Residual plots from the normal linear regression will be examined. If there is any evidence of skew or non-constant variance, repeated measures mixed normal linear regression of log-transformed eGFR will be used to assess whether mean log- eGFR are different between the two treatment arms, adjusting for donor type (living vs deceased donor), participant weight pre transplant (<20kg vs ≥20kg pre-transplant) and participant and transplant centre as random effects.

A separate mixed Normal linear regression will be used to assess whether mean eGFR is different between the two treatment arms at day 90, adjusting for donor type (living vs deceased donor), participant weight pre transplant (<20kg vs ≥20kg pre-transplant) and transplant centre as a random effect. Residual plots from the normal linear regression will be examined. If there is any evidence of skew or non-constant variance, mixed normal linear regression of log-transformed eGFR at 90 days will be used to assess whether mean log-eGFR are different between the two treatment arms, adjusting for adjusting for donor type (living vs deceased donor), participant weight pre transplant (<20kg vs ≥20kg pre-transplant) and transplant centre as a random effect.

Other electrolyte abnormalities within the first 72 hours post transplantation This includes the following:

- Hypernatraemia (defined as plasma sodium concentration > 145mmol/l)
- Hyperkalaemia (defined as plasma potassium concentration > 5.5mmol/L)
- Hypokalaemia (defined as plasma potassium concentration < 3.5mmol/L)
- Non anion-gap acidosis (defined as plasma bicarbonate < 20mmol/L and anion gap < 20mmol/L. Anion gap will be calculated as the sum of plasma sodium and plasma potassium, minus the sum of plasma chloride and plasma bicarbonate).
 Where possible, these components should be obtained simultaneously, but where this is not possible, samples should be collected within an hour.
- Hyperglycaemia (defined as random blood glucose > 5.5 mmol/L)

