- Hypomagnesaemia (defined as plasma magnesium concentration < 0.7 mmol/L)
- Hyperchloraemia (defined as plasma chloride concentration > 107mmol/L)
- Excessive rate of reduction in plasma sodium concentration (defined as >1mmol/L/hour averaged over 6 hours)
- Excessive magnitude of reduction in plasma sodium concentration (defined as > 10mmol/L from pre-transplant level)

The number and percentage of participants who experience each of these events will be presented by trial arm and overall, alongside the median and interquartile range of the number of each event experienced. To test for differences in the proportion of participants experiencing each event, separate mixed logistic regression models will be used. These will be adjusted for donor type (living vs deceased donor), participant weight (<20kg vs ≥20kg pre-transplant) and transplant centre as a random effect. The adjusted odds ratio for treatment, with 95% confidence interval, will be presented from this model, with the p-value from the likelihood ratio test when including and excluding the treatment term from the model.

Maximum and minimum systolic blood pressure

The minimum and maximum systolic blood pressure will be taken for each day, for the first 3 days post-transplant (the measurement recorded in the database will have been sustained on 3 repeated values on each day). The values will be normalised to age and height percentile by the statistician, using the process as specified in https://www.nhlbi.nih.gov/files/docs/resources/heart/hbp ped.pdf and

Statistical Analysis Plan

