4.9 Figures

Figure XX Consort diagram

[figure not shown]

Figure XX Time to first acute hyponatraemia

A cumulative incidence curve showing the time to first developing acute hyponatraemia (defined as plasma sodium concentration <135mmol/L) within 72 hours post-transplant, by arm. Acute hyponatremia will be considered as the event and death prior to the event will be considered as the competing risk. Although if there are no deaths, the Kaplan-Meier method will be used.

Statistical Analysis Plan

Figure XX Lowest plasma sodium concentration by day

For each participant, the lowest plasma sodium measurement each day will be obtained and of these the median and interquartile range will be plotted by day and treatment arm. These will be plotted as box plots, for baseline and for the three days post-transplant. Any outliers will also be populated.

Figure XX Highest plasma chloride level by day

For each participant, the highest plasma chloride measurement each day will be obtained and of these the median and interquartile range will be plotted by day and treatment arm. These will be plotted as box plots, for baseline and for the three days post-transplant. Any outliers will also be populated.

Figure XX Highest potassium level by day

For each participant, the highest plasma potassium measurement each day will be obtained and of these the median and interquartile range will be plotted by day and treatment arm. These will be plotted as box plots, for baseline and for the three days post-transplant. Any outliers will also be populated.

5. Statistical Analysis Plan Amendments

Revision History:

| Version | Author | Date | Reason for revision |
|---------|-------------|------------|--|
| 1.1 | [name] | 20/12/2022 | Updating sensitivity outcomes to incorporate blood gas results as well as plasma. Updating blood pressure outcome to normalised percentile in Table 4.4 in line with text. Separated secondary outcome tables into multiple smaller tables. Clarified some statistical methods/model fitting criteria, including how the planned models will be modified if issues with model fitting. |
| | | | |
| | | | |
| | | | |
| | | | |

6. References

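### The models for the other electrolyte abnormalities omit the child's pre-transplant value of the same analyte, which gives up power that scheduled baseline bloods could supply

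*SAP*

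**What the plan says.** Section 3.4 lists nine other electrolyte abnormalities in the first 72 hours. For the proportion of children with each one, "separate mixed logistic regression models will be used", and the covariates are fixed: "These will be adjusted for donor type (living vs deceased donor), participant weight (<20kg vs ≥20kg pre-transplant) and transplant centre as a random effect". This follows the general rule in section 3.2: "All analyses will be adjusted for the stratification variables (site and participant weight pre transplant: <20kg and ≥20kg) and donor type: deceased and living".

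Seven of the nine are threshold events: hypernatraemia, hyperkalaemia, hypokalaemia, non anion-gap acidosis, hyperglycaemia, hypomagnesaemia and hyperchloraemia. A typical definition is "Hyperkalaemia (defined as plasma potassium concentration > 5.5mmol/L". None requires new onset, and none flags a child already beyond the cut-off. The other two concern the rate and the size of a fall in sodium, and the size is "defined as > 10mmol/L from pre-transplant level".

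The visit schedule in section 2.1 marks blood results and venous blood gases at the pre-transplant baseline. Section 4.9 displays daily sodium, chloride and potassium: "These will be plotted as box plots, for baseline and for the three days post-transplant". The sensitivity analyses in section 3.7 add no baseline value to any model, and the baseline tables in section 4.2 list no electrolytes.

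**The concern.** A child's starting potassium, bicarbonate or sodium may well predict whether that child crosses a threshold in the next 72 hours. Section 3.2 already goes beyond the stratification factors by adding donor type because it could affect the outcomes, and it says that conditional effects will be reported. The same reasoning points to the analyte's own baseline. The SAP uses pre-transplant sodium to define one outcome and then leaves it out of that outcome's model.

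The stated objective (section 1.1) is abnormal plasma electrolyte levels in general, so these models carry much of the trial's evidence beyond the primary outcome. They run on about 128 children with no power claim of their own. If a strong predictor is left out, a real difference in, say, hyperkalaemia or acidosis is more likely to be missed, and a null result may be read as reassurance.

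For the seven threshold outcomes there is a related problem of interpretation. A child who starts beyond the cut-off and stays there after transplant is an event in either arm, and no planned table shows how many such children there are.

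**Working it through.** **The plan's own figure.** The SAP sizes only the primary outcome (section 1.6): 59% v 29.5%, two-sided 5%, 90% power, two interim looks, 128 children, 144 after 10% dropout.

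- Per arm, n = [1.96·√(2·0.4425·0.5575) + 1.2816·√(0.59·0.41 + 0.295·0.705)]² / 0.295² = 57.5, so 58 per arm and 116 in total. With continuity correction the total is 130.
- O'Brien-Fleming looks at 70, 100 and 128 give a final critical value of 2.03 (nominal 0.042) and 91.4% power at 128.
- Dropout: 64/0.9 = 71.1, so 72 per arm and 144 in total.

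The stated size holds up, and this point does not affect it.

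**Effect of adding the baseline value.** The SAP gives no baseline-outcome correlation ρ and no event rates for these outcomes, so both are assumed. The model is a latent value L = ρ·b + √(1−ρ²)·e − δ·arm, with b and e standard normal. An event occurs when L exceeds Φ⁻¹(1−control rate), and δ is set to give the intervention rate. There were 64 children per arm and 4,000 simulated trials per setting. The likelihood ratio test for arm was run without and with b. Weight, donor type and centre were in neither model.

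| Assumed rates | ρ | Power without | Power with | Gain (points) |
|---|---|---|---|---|
| 40% v 20% | 0 | 71.6% | 71.6% | 0 |
| 40% v 20% | 0.3 | 70.6% | 72.4% | 1.8 |
| 40% v 20% | 0.5 | 70.3% | 77.3% | 6.9 |
| 40% v 20% | 0.7 | 71.1% | 85.6% | 14.5 |
| 59% v 29.5% | 0.3 / 0.5 / 0.7 | 91.7 / 92.3 / 93.5% | 93.4 / 96.3 / 98.9% | 1.7 / 4.0 / 5.4 |
| 59% v 40% | 0.3 / 0.5 / 0.7 | 57.2 / 57.3 / 56.1% | 59.5 / 65.8 / 75.0% | 2.3 / 8.5 / 19.0 |

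Gains are taken before rounding. The Monte Carlo standard error of one power is about √(0.71·0.29/4000) = 0.7 points. At 59% v 40% and ρ = 0 the run showed 55.5% and 56.8%, although the covariate then carries no information. Gains of 1 to 2 points are therefore at the limit of what these runs resolve.

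**Type I error** (40% in both arms, ρ = 0.3 to 0.7): 5.1 to 6.0% without the baseline value and 5.15 to 5.6% with it.

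**Abnormalities carried over from baseline.** Suppose a share q start abnormal and remain events in both arms, and the rest have rates of 40% v 20%. The observed rates are q + (1−q)·0.40 and q + (1−q)·0.20.

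| q | Observed rates | Odds ratio | Power, 64 per arm |
|---|---|---|---|
| 0 | 40% v 20% | 0.375 | 70% |
| 10% | 46% v 28% | 0.457 | 56% |
| 20% | 52% v 36% | 0.519 | 44.5% |
| 30% | 58% v 44% | 0.569 | 35% |

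A second simulation (1,500 trials per setting) took 20% abnormal at baseline, with 90% of those becoming events. Power was 46% without the baseline value and 58 to 62% with it, against about 71% unadjusted with no carry-over. Adjustment recovers part of the loss and leaves the events in the count.

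**The case against.** The strongest reply is that nothing here is an error. Sections 3.2 and 3.4 agree with each other, and adjusting for stratification factors plus one prespecified covariate is valid. Section 3.2 claims power for the primary outcome only. The gain rests wholly on assumed rates and correlations, and the baseline value's contribution on top of weight, donor type and centre has not been tested. Section 3.8 relies on every adjustment factor always being known, which a laboratory value would not be. All of this stands. It makes the point a moderate one about efficiency but does not remove it.

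Four stronger readings are tempting, and the SAP does not support them.

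- A reader might infer that the odds ratios are biased or that false positives become more likely. Randomisation prevents the first, and the simulated type I error is about 5 to 6% either way.
- A reader might infer that adjustment removes pre-existing abnormalities from the event count. It does not. Equally, a pre-transplant abnormality is not itself an event: it counts only if it persists or recurs within the 72-hour window.
- A reader might extend the carry-over argument to all nine outcomes. The magnitude outcome is already measured from the pre-transplant level and the rate outcome is a change, so for those two the case is power only.
- A reader might take the list of tests in section 1.4 as proof that every analyte is measured at baseline. That list describes post-operative sampling. Baseline sodium, chloride and potassium are confirmed by section 4.9. For bicarbonate, magnesium and glucose there is only the general pre-transplant blood rows in section 2.1.

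**Conclusion.** The point holds as a matter of lost power. None of the nine models contains the analyte's pre-transplant value, no sensitivity analysis adds it, and for at least three analytes the SAP shows that the value will be in hand.

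The size cannot be derived from the SAP. Under assumed rates of 40% v 20% with 64 per arm, the gain is nil at correlation 0, about 2 points at 0.3, about 7 at 0.5 and about 14.5 at 0.7. Over the other assumed rates it is roughly 2 points at 0.3, 4 to 9 at 0.5 and 5 to 19 at 0.7. The comparison between arms stays valid as written. For the seven threshold outcomes, existing abnormalities can also pull the odds ratio towards 1, by an amount that depends on an unknown baseline prevalence. Because these are secondary outcomes with no power claim, the change is worth making but the plan does not fail without it.

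**What to change.** In section 3.4, add to each of these models the last pre-transplant plasma value of the same analyte as a continuous fixed effect, wherever it is collected. Use bicarbonate for non anion-gap acidosis, and sodium for hypernatraemia and the two sodium-fall outcomes. Fill a missing value with the overall mean and add a missing indicator, so that no child is dropped.

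In the separation rules of section 3.2, make this value and its indicator the first terms removed. That also takes the continuous covariate out before the exact logistic step, which handles such covariates poorly. Amend the statement in section 3.8 that all adjustment factors will be known, and update the footnotes to the section 4.4 tables.

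Separately, for the seven threshold outcomes, tabulate by arm how many children were beyond the cut-off before transplant, with the number measured. This makes carry-over visible, which adjustment alone does not.

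The cost is SAP wording and a few lines of code, with no new data where the baseline value is already collected. The downside is one or two extra parameters per model, which may have to be dropped for rare outcomes, so those would see no gain.

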1.2 Patient Eligibility Criteria

Inclusion criteria

- 1. Patients under 18 years of age at the time of transplantation with valid patient/parental consent
- 2. Patients receiving a kidney only transplant from either a living or deceased donor, in a participating UK centre

Exclusion criteria

1. Multi-organ transplant recipients

Statistical Analysis Plan

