1.5 Randomisation and Blinding Procedures

Eligible patients who have consented to participate in the PLUTO trial will be randomised via an interactive web response system, provided by Sealed Envelope. Participants will be randomised in a 1:1 ratio, to the intervention and control groups. Participants will be randomised on admission to hospital for the transplant, once the trial team are confident that the transplant will be proceeding. Before performing the randomisation, the team must re-confirm the consent/assent (it may have been several weeks since initial consent was provided). The eligibility criteria should also be re-checked prior to randomisation and the site name and patient weight must be known. Upon randomisation, the site will be provided with the allocation (Plasma-Lyte or Standard fluid therapy) and the participant's randomisation number, which will be used to identify participants throughout the trial. This number will take the form RXXXX where XXXX is a four digit participant number.

The randomisation will be stratified by transplant centre and patient weight (<20kg vs ≥20kg pre-transplant). Randomisation will further be balanced using blocks of varying, undisclosed sizes. The randomisation list will be produced by the trial statistician using SAS statistical software.

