https://www.who.int/toolkits/growth-reference-data-for-5to19-years will be used to determine the height percentiles. Heights in cm will be converted to inches by dividing by 2.54 and will utilise the height at transplant. The mean minimum and maximum normalised systolic blood pressure, with standard deviation, will be presented separately for each trial arm and overall, for each day. A repeated measures mixed Normal linear regression will be used to assess whether mean percentiles over the three days are different between the two treatment arms, adjusting for donor type (living vs deceased donor), participant weight pre transplant (<20kg vs ≥20kg pre-transplant) and day of measurement. In addition, two random effects will be included in the model to account for individual participant effects and transplant centre. Residual plots from the normal linear regression will be examined. If there is any evidence of skew or non-constant variance, repeated measures mixed normal linear regression of log-transformed percentile will be used to assess whether mean log-percentile are different between the two treatment arms, adjusting for donor type (living vs deceased donor), participant weight pre transplant (<20kg vs ≥20kg pre-transplant) and participant and transplant centre as random effects.

Number of changes in intravenous fluid composition within the first 72 hours post-transplant

A change to intravenous fluid composition will be defined as any modification to the composition of the fluid administered to the participant. The number of changes in fluid will be counted as follows:

- If the participant is initially given something different to which they were randomised, this will be counted as the first change
- Subsequent changes will be counted based on the fluid being administered before the change.
- Diluent used for drug infusions, will not be counted.

For example:

- if the participant was randomised to standard arm, was first administered Hartmann's solution, then 0.9% sodium chloride, and then Hartmann's solution again, this would be counted as two changes.
- If the participant was randomised to Plasma-Lyte, was first administered 5% glucose, then received Plasma-Lyte 148 and then Plasma-Lyte® 148 & Glucose 5%, this would count as three changes.

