3.8 Procedures for handling Missing Data

Any missing primary and secondary outcome data will be summarised. For the primary outcome and other blood test results, the result will be considered missing if there are no results for that measurement within the 72-hour period post transplant. It is anticipated that missing data for the primary outcome will be rare, as the plasma sodium measurement is also used to determine one of the key SAEs within the trial, which mandates immediate reporting. Missing data due to death or withdrawal are also anticipated to be very rare: data from the UKTR showed that the 1-year patient survival rate for those transplanted between 2015-2018 was 99% (95% confidence interval 96-100) for paediatric kidney transplants from living and DBD donors (5). Primary and secondary outcome measures will not be imputed and these will be treated as missing data and excluded from the relevant analyses. If outcome data is missing for more than 25% of participants, outcomes will not be reported.

To explore if missing values have an undue impact on the primary outcome result, a sensitivity analysis using multiple imputation will be performed if the primary outcome is missing in more than 5% of the participants included in the modified intention to treat analysis. Variables will be included in the imputation model if they have a completeness of ≥65% and these variables are:

- Donor: type, age, ethnicity, BMI
- Trial participant/Recipient: age, sex, ethnicity, cause of end stage kidney disease, native urine output, dialysis type, weight and height at transplant, systolic blood pressure, blood group, calculated reaction frequency, graft number
- Transplant: blood group match, transplanting centre, cold ischaemic time, HLA mismatch between donor and recipient, graft placement.

Forty imputations will be used and the average across the imputations will be calculated. The model specified in section 3.3 will be utilised.

If the proportion of participants with a missing primary outcome is less than or equal to 5% then this sensitivity analysis will not be performed.

Statistical Analysis Plan

All the risk adjustment factors will always be known, as weight and site are required for randomisation and donor type is mandatory data required by the UKTR.

4. Data Analysis Tables

Data analysis will be based on the following tables.

- 4.1 Screening, Recruitment and Follow-up tables
 - 4.1.1 Recruitment by Centre

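### Systolic pressure is normalised with a height reference that starts at age 5, and its log-percentile fallback cannot correct left skew and drops the day term

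*SAP*

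**What the plan says.** SAP section 1.2 includes "Patients under 18 years of age at the time of transplantation with valid patient/parental consent". The one exclusion is "Multi-organ transplant recipients", so there is no lower age or weight limit. Section 1.5 stratifies randomisation at 20 kg, so the plan expects small children.

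In section 3.4 the daily minimum and maximum systolic pressures over the first three days are a secondary outcome. "The values will be normalised to age and height percentile by the statistician", and for the height part "https://www.who.int/toolkits/growth-reference-data-for-5to19-years will be used to determine the height percentiles". No other height source is named.

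The main analysis is a repeated-measures Normal mixed model, which "will be used to assess whether mean percentiles over the three days are different between the two treatment arms". It adjusts for donor type, weight group and day of measurement, with random effects for participant and centre. If residual plots show any skew or non-constant variance, "repeated measures mixed normal linear regression of log-transformed percentile will be used to assess whether mean log-percentile are different" between arms. The covariates listed for that fallback are donor type and weight group, with the same two random effects; day is not among them. The eGFR analysis over days 1, 3 and 7 in the same section has the same pattern: day is in the main model and absent from the log fallback.

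Section 3.8 does not impute outcomes, and adds: "If outcome data is missing for more than 25% of participants, outcomes will not be reported".

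**The concern.** A systolic percentile for age and height needs a height percentile first. By its own label, the only height reference named runs from 5 to 19 years. For an eligible child of, say, 3 years, the derivation stops at that step. Either the youngest children silently leave this outcome, or someone picks a reference once the data are in hand. The plan fixes neither.

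The second problem is the scale. A percentile cannot go below 0 or above 100. If pressures run above the reference median, percentiles bunch towards 100 with a tail to the left. The fallback is triggered by skew in either direction, but a log pulls in only a right tail and stretches a left one. The remedy can therefore leave the model fitting worse than the one it replaces.

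Third, if followed literally, switching to the log scale also removes a covariate, so the two analyses differ in more than their scale.

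**Working it through.** The SAP gives no figure of its own on this point, so there is none to reproduce.

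**Step 1. Age coverage.** Eligible: under 18, no minimum (section 1.2). Height reference: 5 to 19 years (section 3.4). Not covered: every participant under 5.

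**Step 2. How many.** The SAP gives no age distribution, so the share is assumed. Count = share × 144 (section 1.6):

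- 10%: 0.10 × 144 = 14.4, about 14
- 20%: 0.20 × 144 = 28.8, about 29
- 30%: 0.30 × 144 = 43.2, about 43
- 40%: 0.40 × 144 = 57.6, about 58

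The modified intention-to-treat set counts only transplanted participants. On the 128 that section 1.6 requires before drop-out, 10% to 40% is about 13 to 51.

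**Step 3. Effect of the log.** Let z be the systolic z-score, assumed Normal with mean mu and SD 1. The percentile is P = 100 × Φ(z). Skewness of P and of log P is compared over a range of mu, because the SAP gives no blood pressure data. The floored column uses 1,000,000 draws with P floored at 0.1 before taking logs. The last column is the same quantity without a floor, by numerical integration of log(100 × Φ(z)) over the Normal density.

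| mu | Skewness of P | log P, floored at 0.1 | log P, no floor |
|---|---|---|---|
| -1.5 | +1.80 | -0.58 | -1.21 |
| -1.0 | +1.10 | -1.03 | -1.41 |
| -0.5 | +0.52 | -1.45 | -1.67 |
| 0 | 0.00 | -1.90 | -2.00 |
| +0.5 | -0.52 | -2.41 | -2.44 |
| +1.0 | -1.10 | -2.98 | -3.03 |
| +1.5 | -1.80 | -3.84 | -3.85 |

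The row mu = 0 can be checked exactly. There P/100 is uniform, minus its log is exponential with skewness 2, and so the log has skewness -2.

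For every mu at or above 0 the log moves the distribution further from symmetry. At mu = -0.5 it replaces mild right skew with larger left skew. At mu = -1 it roughly exchanges one skew for the other. At mu = -1.5 it reduces the size of the skew.

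**Step 4. Where the log helps.** That is the region of percentiles near 0. The SAP does not say whether percentiles are kept to whole numbers. If they are, P rounds to 0 with probability Φ(-2.576 - mu): 0.5% at mu = 0, 5.7% at mu = -1 and 14.1% at mu = -1.5. The log of 0 is undefined, and the SAP has no rule for it.

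**Step 5. z-score.** Φ⁻¹(P/100) returns z, with skewness 0 here. That follows from the Normal assumption and is not evidence from data, but the z-score is unbounded and has no pile-up at the limits.

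**Step 6. Day term.** Main systolic model: day in. Log systolic model: day not listed. Main eGFR model over days 1, 3 and 7: day in. Log eGFR model: day not listed. With every participant measured on every day, the treatment estimate on a given scale would not change, since it compares participants' means. With unequal missing days it can change. In both cases any day trend enters the residuals.

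**The case against.** **Exclusion.** A reader might infer that the SAP excludes children under 5 from this outcome. It does not: section 3.2 defines the efficacy population as all randomised and transplanted participants, and nothing removes anyone by age. What stands is that the derivation cannot be completed for them as written.

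**Non-reporting.** A reader might also infer that the outcome will go unreported under the 25% rule. That needs more than 0.25 × 144 = 36 participants without a value, and the share under 5 is unknown; the 20 kg stratum is about weight, not age. It also needs an underivable percentile to count as missing. Section 3.8 defines missing only for blood results, and the table in section 4.8 lists the recorded pressures, with no row for the normalised value. The consequence is possible but not established, and the rule itself is a separate matter.

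**Skew.** A third tempting reading is that the fallback always worsens skew. The table shows otherwise at mu = -1.5, and the daily minimum could lie there. The SAP also inspects model residuals, whereas the table gives marginal skewness. The direction of the argument survives, because a log compresses the upper tail and stretches the lower one whatever the starting shape. The sizes are illustrative.

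**Percentiles are deliberate.** The revision history aligned the results table with the percentile wording. That is a fair reason to keep percentiles as a description. It does not make the log of a percentile a sound fallback.

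**The day term** may be a drafting slip, since the fallback is still called repeated measures. That is a reason to correct the text, not to leave it.

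**Conclusion.** The point holds in three parts.

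1. No height reference is specified below age 5 in a trial with no lower age limit. This follows from the SAP's text, taking the reference's coverage from its own label. The number affected is unknown; about 14 to 58 of 144 rests on an assumed share of 10% to 40%.
2. The log-percentile fallback cannot correct left skew and makes it worse. The sizes (0.00 to -1.90 at mean z of 0, and -1.10 to about -3.0 at +1) rest on an assumed Normal z-score with SD 1. The log helps only when percentiles cluster near 0, where whole-number zeros cannot be logged.
3. Both repeated-measures log fallbacks omit the day term of their main models.

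This concerns secondary outcomes and the primary analysis is untouched. It should be settled before analysis, because otherwise the handling of the youngest children is decided after the data are seen.

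**What to change.** In SAP section 3.4:

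- Name a height reference, or references, covering every eligible age including under 5, and state the age at which one hands over to the other.
- Replace the log-percentile fallback with an analysis of the systolic z-score, the inverse Normal of the percentile. Keep the percentile unrounded, because 0 and 100 have no finite z-score. Percentiles by arm and day can still be shown descriptively.
- Add day of measurement to the fallback models for systolic pressure and for eGFR over days 1, 3 and 7.

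The cost is SAP wording and a second look-up table, with no new data. The drawback is a treatment effect in z-score units, which clinicians read less easily than percentiles; the descriptive percentiles offset this in part.
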